**Table 5-1 Imputation of start dates**

Missing elements	Rule
Day, month, and year	
The date uncertainty is too high to impute a rational date. Therefore, if the year value is missing, the imputed start date is set to NULL.

Day and month	

• If available year = year of study treatment start date then

– If end date contains a full date and end date is earlier than study treatment start date then set start date = 01JanYYYY

– Else set start date = study treatment start date.

• If available year > year of study treatment start date then 01JanYYYY

• If available year < year of study treatment start date then 01JulYYYY

Day	

• If available month and year = month and year of study treatment start date then

– If end date contains a full date and end date is earlier than study treatment start date then set start date= 01MONYYYY.

– Else set start date = study treatment start date.

• If available month and year > month and year of study treatment start date then 01MONYYYY

	

• If available month and year < month year of study treatment start date then 15MONYYYY

--	--

### **5.1.3 Concomitant medication date imputation**

The same rule as AE imputation will be applied.

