## Prior and Concomitant Medication

Prior medication will be defined as any non-study medication taken prior to the first dose of the study drug, irrespective of whether the medication continued into the treatment period.

Any non-study medication administered at least once between the day of first dose of study drug and end of the study will be a concomitant medication.

Therefore, some medications can be categorized as both, prior and concomitant medication.

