### **Listings**

## **2.4.2 A listing showing exposure in doses and days. Prior, concomitant and post therapies**

Please refer to [Section 2.1.1](#) for the definition of prior and concomitant medication.

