#### 5.1.2 AE date imputation

To decide whether the event was prior or post-dosing is carried out as follows:

- If start date and time are not missing, then report as post-dosing if start date and time > dosing start date and time
- If start date is available, but not start time, then report as post-dosing if start date > dosing start date. This means that all events occurring on the dosing start day (even if they occurred prior to it) will be considered as post-dosing.
- If both start date and time are missing, the event will be defined as being post-dosing.

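### SAP 5.1.3 reuses the AE date rule for medications, so some ongoing drugs are lost from the prior table; separately, the concomitant window in 2.1.1 runs to study end and differs in length by arm

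*SAP*

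**What the plan says.** SAP 5.1.3 covers medication dates in one sentence: "The same rule as AE imputation will be applied." The rule it borrows has two parts.

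- SAP 5.1.2 sorts events into before and after dosing: "If both start date and time are missing, the event will be defined as being post-dosing."
- SAP Table 5-1 imputes partial start dates. With no year, "if the year value is missing, the imputed start date is set to NULL." With only the year known, and equal to the year of first dose, it looks at the stop date first: "If end date contains a full date and end date is earlier than study treatment start date then set start date = 01JanYYYY." Failing that, "Else set start date = study treatment start date." The row for a missing day works the same way within the month of first dose. For an earlier year, the entry ends "year of study treatment start date then 01JulYYYY"; for an earlier month, the start becomes the 15th of that month.

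SAP 2.1.1 defines prior medication as any non-study drug used before first dose, whether or not it continued. Any non-study drug "administered at least once between the day of first dose of study drug and end of the study will be a concomitant medication." A drug can be both.

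SAP 2.4.2, whose heading includes "Prior, concomitant and post therapies", plans counts and percentages of participants with concomitant medication by ATC class and preferred term, by arm and overall, and a similar table for prior medication.

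Protocol 6.2.1 collects medications from 6 months before Screening. Protocol 12.3 plans summaries of medications before and after the start of study treatment.

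**The concern.** Counting an AE of unknown onset as post-dosing is cautious, because the event is then included among those possibly due to the drug. A medication carries no such asymmetry. A participant's background drug with no recorded start is more likely to be old than new: the protocol expects permitted chronic drugs to have been stable for at least 6 weeks before first dose. The AE default moves that drug to the wrong side of first dose.

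The second matter is the length of the concomitant window. Dosing stopped for the whole trial by 08-Aug-2022, medication restrictions were later lifted, and only the branaplam arm was asked to stay for about a year. Use recorded in that year goes into the same table as use during dosing.

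The study was stopped for neurotoxicity, so a reader will want to know whether a drug preceded, accompanied or followed branaplam. SAP 2.4.2 specifies summary tables and no dated medication listing from which timing could be recovered.

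**Working it through.** There is no planned figure to reproduce. The check is to run the stated rules on possible date patterns, then do date arithmetic for the window.

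**Classification.** The first dose is taken as 15-Mar-2022 for illustration only. The imputed start follows Table 5-1. Prior and concomitant follow 5.1.2 and 2.1.1.

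| Start recorded | Stop recorded | Imputed start | Prior? | Concomitant? |
|---|---|---|---|---|
| missing | ongoing | none | no | yes |
| missing | 05-Mar-2022 | none | no, by 5.1.2 | 5.1.2 post-dosing; 2.1.1 no |
| missing | Feb 2022, day unknown | none | no | yes |
| 2022 only | ongoing | 15-Mar-2022 | no | yes |
| 2022 only | 05-Mar-2022 | 01-Jan-2022 | yes | no |
| 2022 only | Feb 2022, day unknown | 15-Mar-2022 | no | yes |
| Mar 2022 | ongoing | 15-Mar-2022 | no | yes |
| Mar 2022 | 05-Mar-2022 | 01-Mar-2022 | yes | no |
| 2019 only | ongoing | 01-Jul-2019 | yes | yes |
| Feb 2022 | ongoing | 15-Feb-2022 | yes | yes |

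Four results follow.

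1. An ongoing drug with a wholly missing start, or with a partial start in the year or month of first dose, is lost from the prior table.
2. Partial starts in an earlier year or month stay prior.
3. The stop-date guard in Table 5-1 works for a partial start when the full stop date is before first dose. It cannot act on a partial stop date, and the SAP has no imputation rule for medication stop dates.
4. For a wholly missing start with a full stop date before first dose, 5.1.2 and 2.1.1 disagree.

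If 5.1.3 imports only Table 5-1 and not the 5.1.2 bullets, a wholly missing start is left null and its prior status is undefined.

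**Window.** Inputs: last treatment in the trial on 08-Aug-2022, and about one year of follow-up after last dose for branaplam participants (Protocol, Amendment 02 rationale); Week 69 at day 477 and Week 33 at day 225 (Protocol Table 8-5); on treatment up to last dose + 13 days (SAP 2.1.1, written for listed assessments and not for medications).

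Off-drug share = 1 − [(08-Aug-2022 − Day 1) + 1 + 13] / 477. The Day 1 dates below are assumptions. Each row also assumes that the participant's last dose was on 08-Aug-2022 and that follow-up reached day 477.

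| Assumed Day 1 | On-treatment days | Off-drug share |
|---|---|---|
| 08-Dec-2021 | 243 + 14 = 257 | 46% |
| 01-Mar-2022 | 160 + 14 = 174 | 64% |
| 27-Apr-2022 | 103 + 14 = 117 | 75% |
| 15-Jun-2022 | 54 + 14 = 68 | 86% |

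A date in the documents points the same way. The SAP history places 26-Oct-2023 before last participant last visit, which is 444 days (444/7 ≈ 63 weeks) after the last dose.

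By schedule, a branaplam participant's window can reach day 477. A placebo participant's may end at day 225 (477/225 ≈ 2.1 times shorter) or, if Week 33 had already been completed, at once.

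**The case against.** The strongest reply is that most date patterns come out right. A long-standing drug whose start is roughly recalled will usually have an earlier year or month, and Table 5-1 keeps it prior. A drug known to have ended before first dose is normally kept out of the concomitant table, either by the stop-date guard or by the 2.1.1 definition itself. An ongoing drug is never lost from the concomitant table. All of this stands, and it limits the point to the patterns shown above.

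A reader might go further and infer that chronic drugs in general disappear from the prior table, or that drugs finished before dosing are routinely shown as concomitant. The documents support neither. A reader might also infer that background therapy will be presented as newly started. The planned tables carry no start timing and no such category; the drug is only missing from the prior table.

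On the window, 2.1.1 says openly that it runs to study end, and Protocol 12.3 splits medications only at the start of treatment. The SAP therefore does not contradict the protocol, and the table does not claim that every listed drug was taken together with branaplam. The TEAE definition in SAP 2.7.1 also states no end. Cutting the concomitant class at last dose + 13 days would remove drugs from a period whose AEs are still counted. That is a sound reason to keep the overall table. It does not answer the unequal follow-up by arm, or the fact that the 2.4.2 heading names post therapies which are neither defined nor tabulated.

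**Conclusion.** The point holds in limited form. As written, the SAP puts an ongoing drug in the wrong class for prior use when the start is wholly missing (or leaves its status undefined, if only Table 5-1 is imported) or is partial within the year or month of first dose. It conflicts with itself for a wholly missing start with a full stop date before first dose, and has no working rule for a partial stop date. Separately, because of the 2.1.1 definition and not because of 5.1.3, the concomitant percentages mix on-drug and off-drug use over follow-up that is longer in the branaplam arm.

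Only descriptive medication tables are affected. It might be inferred that efficacy or safety results change, but no planned analysis uses the prior or concomitant flag. The number of affected records is unknown. The 46% to 86% range illustrates calendar time under assumed first-dose dates and is not a count of medications. The change is worth making because it corrects a stated rule and needs no new data.

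**What to change.** Rewrite 5.1.3 with its own rule for medications:

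1. Check the stop date first, full or partial. If its known parts fall before first dose, the drug is prior only.
2. Otherwise, treat a wholly missing start as both prior and concomitant.
3. For an ongoing drug whose partial start lies in the year or month of first dose and cannot be placed before or after it, count the drug as both prior and concomitant.
4. Leave the Table 5-1 handling of earlier years and months as it is.

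In 2.1.1 and 2.4.2, keep the overall concomitant table and add a split by arm. One class holds drugs taken from first dose to last dose + 13 days, which extends the SAP's on-treatment rule to medications. The other holds drugs first started later, labelled post-treatment. This gives the post therapies in the heading a definition and a table.

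The cost is a few sentences and one extra table from data already collected. The drawback is that a few drugs truly started after dosing, but with ambiguous partial dates, will also be counted as prior.

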### **5.1.4 Values below LLOQ**

For biomarker parameters, values below the lower limit of quantification (LLOQ) will be set to LLOQ/2 for statistical analysis. LLOQ value may differ across samples. For statistical analysis, the sample specific LLOQ and ULOQ value should be used.

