Population	
Approximately 75 male or female patients with confirmed Stage 1 or 2 HD and a UHDRS total functional capacity (TFC) score of >8 will be enrolled in this study to allow for approximately 25 participants per treatment arm. Fewer participants will be enrolled if all treatment arms are not opened.
 
Manifest patients with a TFC >8 are selected because they are late enough in the disease process so that mHTT can be measured in their CSF and clinical symptoms can be readily assessed, and early enough in the disease process so that they can comply with the protocol defined schedule of assessments during Core blinded treatment period (DRF and BE) and be monitored for disease progression and safety throughout the OLE. Eligible patients starting at the age of 25 will be enrolled to avoid the very high CAG repeats associated with early disease onset as these patients could be considered to have a more rapidly progressing phenotype. An age cap of 75 years is employed to avoid age-related comorbidities that typically occur above this age.

Key Inclusion criteria	
As per the USM follow-up notification dated 06-Dec-2022, no further participants will be enrolled in this study.
 
Participants eligible for inclusion in this study must meet all of the following criteria:
 
 1. Signed informed consent must be obtained prior to participation in the study. 2. Must be capable of providing informed consent (in the opinion of the Investigator). 3. Clinically diagnosed Stage 1 or 2 Huntington's disease with a diagnostic confidence level (DCL) = 4 and a Unified Huntington's Disease Rating Scale (UHDRS) Total Functional Capacity (TFC) >8 at screening. 4. Genetically confirmed Huntington's disease, with presence of ≥ 40 cytosine-adenine-guanine (CAG) repeats in the huntingtin gene. 
For participants without prior documentation, a sample must be sent to the central study laboratory and confirmation of the CAG repeat length for these participants must be obtained prior to randomization.
 
For participants with previously existing documentation of their CAG repeat length, it is acceptable to use this prior data to qualify for randomization. These participants must also submit a sample for CAG repeat testing to be conducted by the central study laboratory.
 
 5. Male and female participants between 25 to 75 years of age, inclusive, on the day of Informed Consent signature.

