2.1 Primary estimands

As per the USM follow-up notification dated 06-Dec-2022, the original estimand definition for dose-response relationship is no longer applicable due to permanent discontinuation of study treatment, and no dose-response modelling will be done. The primary endpoint mHTT in CSF will be summarized descriptively as specified in [Section 12](#).

The clinical question of interest is the effect of branaplam versus placebo on percent reduction of mHTT protein in CSF from baseline to Week 17 when the assigned treatment had been taken over 16 weeks with only limited interruptions or discontinuation (as defined below) in patients with manifest HD, mHTT protein in CSF above a detectable level, and a UHDRS TFC score of >8.

The primary estimand is described by the following attributes:

1. Population: male or female patients with confirmed Stage 1 or 2 HD (manifest), mHTT protein in CSF above detectable level, and a UHDRS TFC score of >8 in line with protocol defined I/E criteria. Further details about the population are provided in [Section 5](#).
2. Primary variable: change from BL (%) to Week 17 in mHTT protein in CSF.
3. Treatment of interest: the randomized treatment (allowed medication and prohibited medication see [Section 6](#)) taken for the DRF period (16 weeks of treatment) with a maximum of 25% missed doses (i.e., 4 doses for weekly dosing during DRF period) AND less than 2 consecutive weeks off treatment prior to the Week 17 visit LP.

Handling of remaining intercurrent events:

- Treatment discontinuations or interruptions of dosing beyond acceptable limits for any reason: the treatment effect will be imputed as if the treatment had continued or dosing had not been interrupted (hypothetical strategy). The limit is reached if one or both of the criteria below are met:
 - >25% missed doses (i.e., > 4 doses for weekly dosing during DRF period)
 - 2 or more consecutive weeks off treatment prior to week 17 (LP)
- Intake of prohibited medications without discontinuation of study drug: the treatment effect will be imputed as if the prohibited medications had not been taken (hypothetical strategy)

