5.1 Inclusion criteria

Participants eligible for inclusion in this study must meet **all** of the following criteria:

1. Signed informed consent must be obtained prior to participation in the study.
2. Must be capable of providing informed consent (in the opinion of the Investigator)
3. Clinically diagnosed Stage 1 or 2 Huntington's disease with a diagnostic confidence level (DCL) = 4 and a UHDRS Total Functional Capacity (TFC) >8 at screening
4. Genetically confirmed Huntington's disease, with presence of ≥ 40 CAG repeats in the huntingtin gene.
 - For participants without prior documentation, a sample must be sent to the central study laboratory and confirmation of the CAG repeat length for these participants must be obtained prior to randomization
 - For participants with previously existing documentation of their CAG repeat length, it is acceptable to use this prior data to qualify for randomization. These participants must also submit a sample for CAG repeat testing to be conducted by the central study laboratory.
5. Male and female participants between 25 to 75 years of age, inclusive, on the day of Informed Consent signature

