**Figure 1-1 Study Design Overview**

#### 1.1.1 Primary estimand(s)

Not applicable due to early termination.

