## 2.2 Analysis sets

The **Screened** set will consist of all screened participants.

The **Randomized Analysis Set (RAS)** will consist of all participants who received a randomization number, regardless of whether participants received study medication.

The **Full Analysis Set (FAS)** will consist of all randomized participants who received at least one dose of study drug.

The **Safety Set (SAF)** will consist of all participants who received at least one dose of study drug. All analysis will be conducted on SAF except PK related analysis.

The **PK analysis set** will consist of all participants with at least one evaluable concentration data sample. All PK analysis will be conducted on PK analysis set.

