### **2.5.1 Primary endpoint(s)**

### **2.5.2 Statistical hypothesis, model, and method of analysis**

The efficacy primary endpoint is the % change from baseline of mHTT protein concentration in CSF at week 17, which is expressed as:

$$(mHTT_{wk17} - mHTT_{baseline}) / mHTT_{baseline} * 100\%$$

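### SAP 5.1.4 lets a baseline CSF mHTT value imputed as LLOQ/2 become the denominator of the primary % change; the SAP should not calculate the ratio in that case

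*SAP*

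**What the plan says.** After the Urgent Safety Measure, both documents drop the dose-response estimand and keep CSF mHTT as a descriptive endpoint. SAP 2.5.2 reads: "The efficacy primary endpoint is the % change from baseline of mHTT protein concentration in CSF at week 17", with the baseline value as the divisor. SAP 2.5.2 and 2.11.2 call for summaries of raw values, change, % change and annualized % change by visit, the active-placebo difference in % change, and plots of individual and mean % change.

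For biomarker parameters, SAP 5.1.4 states that "values below the lower limit of quantification (LLOQ) will be set to LLOQ/2 for statistical analysis. LLOQ value may differ across samples". It adds that the sample-specific limit is to be used. It does not separate baseline from post-baseline samples, or raw values from ratios.

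SAP 2.2 fixes the population: "All analysis will be conducted on SAF except PK related analysis". SAF is the Safety Set, meaning everyone who took at least one dose.

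Two protocol texts concern whether mHTT can be measured. Protocol 2.1 describes the population of the pre-termination estimand as having "mHTT protein in CSF above detectable level, and a UHDRS TFC score of >8 in line with protocol defined I/E criteria". The rationale for enrolling manifest patients with TFC above 8 (protocol summary and Section 5) is that "they are late enough in the disease process so that mHTT can be measured in their CSF".

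**The concern.** Half the LLOQ is a common stand-in for a low value in a summary of concentrations. As a divisor it does something else, because the ratio is then scaled by the assay limit and not by the participant's own starting level. A participant who responded to the drug could show no change or a doubling.

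At stake are the mean % change in CSF mHTT, its annualized version and the active-placebo difference. Cohort 1 is small and its placebo group very small, so one artefact ratio can be visible in a group mean. The SAP plans no sensitivity or supplementary analysis for this endpoint (SAP 2.5). It does guard comparable summaries elsewhere: the geometric mean of PK concentrations is not calculated if any value is zero (SAP 2.6.2.3), and volumetric MRI summaries are repeated without participants who had a subdural hematoma (SAP 2.6.2.2).

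**Working it through.** **1. The plan's own figure.** The only computed figure tied to this endpoint is average power above 80% (Protocol 12.8.1). With its inputs (doses 0, 56, 112 and 154 mg; n = 15, 20, 20, 20; 35% lowering at the top dose; SD 0.471 placebo and 0.195 active, read as already inflated; one-sided 5%), the multiple-contrast test gives an average of 89.1%. The figure is reproduced, and nothing below depends on it.

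**2. Does another rule catch an unquantifiable baseline?**
- Entry criteria (Protocol 5.1, 5.2): no CSF mHTT requirement. The nearest is clinical: "and a UHDRS Total Functional Capacity (TFC) >8 at screening".
- Baseline definition (SAP 2.1.1): the last pre-treatment assessment, with no quantifiability condition.
- Analysis sets and exclusions (SAP 2.2, Table 5-16): consent, randomization and dosing only.
- Missing-data rule (SAP 2.5.4): covers missing values, and a value set to LLOQ/2 is not missing.

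None of these stops the imputed value from reaching the denominator.

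**3. One participant.** Let L be the LLOQ of the baseline sample and W the Week 17 value. Baseline becomes L/2, so

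% change = (W - L/2) / (L/2) x 100 = (2W/L - 1) x 100.

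- W below the same LLOQ, so W = L/2: 0%.
- W = L: +100%. W = 1.25L: +150%. W = 2L: +300%. Any W at or above L gives at least +100%.
- Both below LLOQ, with the Week 17 LLOQ r times the baseline LLOQ: (r - 1) x 100, which is -50% for r = 0.5 and +100% for r = 2.

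**4. Annualized % change.** SAP 2.1.1 multiplies by 365.25 and divides by the interval in days plus one. From Day 1 (the pre-dose CSF sample in Protocol Table 16-7) to Day 113 the divisor is 113, and 365.25/113 = 3.23. A +100% artefact becomes about +323%.

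**5. Group means.** Assumptions: 25 participants split 4:1 into 20 active and 5 placebo (the planned size; the actual numbers are not in the documents). The other active participants average -30%, close to the lowering reported in the Amendment 02 rationale, and the other placebo participants average 0%. One participant has a baseline below LLOQ.

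| Group | Week 17 of that participant | Group mean |
|---|---|---|
| Active | below the same LLOQ | (19 x -30 + 0)/20 = -28.5% |
| Active | at the LLOQ | (19 x -30 + 100)/20 = -23.5% |
| Placebo | below the same LLOQ | (4 x 0 + 0)/5 = 0% |
| Placebo | at the LLOQ | (4 x 0 + 100)/5 = +20% |

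With the other group unchanged, the active-placebo difference of -30 points becomes -23.5 in the second row and -30 - 20 = -50 in the fourth. The artefact can therefore hide or inflate lowering.

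**6. How much of this is imputation?** Suppose the true baseline is bL, with b between 0 and 1, and Week 17 is at L. The true change is (1/b - 1) x 100. At b = 0.5 it is +100% and the imputation is right. As b approaches 1 it approaches 0%, so the imputation adds up to 100 points: 100/20 = 5 points on the active mean and 100/5 = 20 on the placebo mean. Below b = 0.5 the imputation understates the rise. So at most 5 of the 6.5 points between -30% and -23.5% are due to the imputation. In placebo, all 20 points can be.

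**The case against.** The strongest reply is that this may never happen. The documents report no baseline below LLOQ, and the population was chosen in the expectation that mHTT would be measurable. LLOQ/2 is a general rule fixed in the SAP, and applying it to baseline mHTT is an inference from its wording. The analysis is descriptive, so no test or error rate is involved. The default summaries include median, quartiles, minimum and maximum, and raw values and individual plots are produced, so in about 25 participants a value of +100% or more would be noticed. All of this stands, and it limits the point to a conditional one. It does not remove the point. The SAP itself provides for values below LLOQ and for limits that vary between samples, the rule as written covers baseline, and a forced 0% would not stand out in any plot or range.

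A reader might infer that the plan breaks its own primary estimand, since Protocol 2.1 asks for detectable mHTT and no entry criterion enforces it. The documents do not support that as a live defect. The condition sat in the population attribute and was not part of the primary variable. The protocol now says that "the original estimand definition for dose-response relationship is no longer applicable due to permanent discontinuation of study treatment", and SAP 1.1.1 says "Not applicable due to early termination". The old text shows only an original intent to study patients with detectable CSF mHTT. Nor would restricting to quantifiable baselines recreate that population, because a value can be detectable and still below the LLOQ.

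**Conclusion.** The point holds in conditional form. Followed as written, SAP 5.1.4 turns a baseline below LLOQ into a % change that the assay limits largely determine, and no other rule intervenes. Under the assumptions in the working, one such participant moves the active mean from -30% to between -28.5% and -23.5% when Week 17 is at or below a shared LLOQ, and can move the placebo mean from 0% to +20%. Higher Week 17 values move it further, though part of that movement would be a real rise. If no baseline is below LLOQ, nothing changes.

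Two stronger readings are not supported. First, one might infer that the reported mHTT result is in fact distorted, perhaps because SAP 2.6.2 withholds the other HTT biomarkers over assay problems. The SAP does not extend those problems to CSF mHTT, and the documents give neither its LLOQ nor a count of low baselines. Second, one might take this to be the trial's only efficacy result. The UHDRS scores and volumetric MRI are also summarised; CSF mHTT is the primary efficacy endpoint.

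The correction is worth making because it is cheap and concerns the primary endpoint.

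**What to change.** In SAP 2.5.2 and 2.11.2, state that % change and annualized % change in CSF mHTT are not calculated when the baseline value is below its LLOQ, and that these participants do not contribute to the active-placebo difference in % change. Report their number by arm. Keep them in the raw-value and absolute-change summaries and in any listing: absolute change has no denominator, and an imputed baseline can shift it by at most LLOQ/2. Keep LLOQ/2 for post-baseline values, and flag those values in the tables and individual plots.

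The cost is about two sentences and a count. There are two downsides. The n for % change may be slightly smaller. Requiring a quantifiable baseline also selects on a noisy measurement, which near the LLOQ can bring some regression to the mean, toward apparent lowering, in both arms. The sponsor study team was unblinded on 02-Nov-2022 (Protocol 6.4), before the October 2023 SAP versions, so the rule should depend only on the pre-treatment sample, as this one does.
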